2.2 Primary Study Endpoints

Demonstrate that coordination of HBO with SRS treatments is feasible.

For HBO sensitization of SRS patients to be feasible, patients must receive radiation treatment within a time frame in which pO₂ levels are meaningfully elevated. Since intratumoral oxygen levels within the brain remain elevated for about 30 minutes after exposure to hyperbaric oxygen [17], feasibility of HBO-SRS treatment requires that a patient at least begin SRS within 30 minutes of leaving the HBO chamber. Evaluation of the ability to achieve this goal will be the primary study endpoint. We will measure time from end of “dive” to start of SRS treatment. Goal will be to achieve “beam on” within 15 minutes of leaving the chamber. Total time for treatment to one isocenter (from first arc’s beam-on to last arc’s beam-off) using SRS in this study is estimated at 10 minutes (three SRS arcs, each 2 minutes, plus set-up time between the first and second and between the second and third arcs, each 2 minutes, totaling 10 minutes). We anticipate a learning-curve as HBO and therapy staff to develop skill sets for optimizing time across the various steps of the procedure:

- Leaving the HBO chamber
- Fitting the - [VisionRT open face mask system](#)
- Positioning the patient on the table
- Imaging the patient to confirm position
- Reviewing/approving images for treatment

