2.3 Secondary Study Endpoints

Demonstrate that outcomes for HBO combined with SRS treatment are non-inferior to historical controls.

Secondary endpoints will include:

- Symptomatic treatment toxicity. Every patient who receives treatment on this protocol will be evaluated for solicited adverse events. “Solicited adverse events” are predefined side effects/medical occurrences identified by the PI and co-PIs to be potentially related to intracranial SRS and/or HBO treatments. These are enumerated in Attachment 14.6. These will be graded using the

Common Toxicity Criteria Adverse Events (CTCAE) v4.0 of the National Cancer Institute. These will be analyzed in one of two categories:

- Acute toxicities
 - Neurological toxicities
 - Other toxicities
- Chronic toxicities
 - Neurological toxicities
 - Other toxicities
- Radiographic evidence for radionecrosis/treatment effects in normal tissue, as defined by review/analysis by diagnostic radiologist of follow-up MRI imaging
- Incidence of whole brain radiation therapy (WBRT)
- Incidence of repeat SRS to the index site
- Incidence of repeat SRS to a distant site
- Local disease recurrence at the treatment site, as defined by review/analysis by diagnostic radiologist of follow-up MRI imaging
- Distant disease recurrence elsewhere in the brain, as defined by review/analysis by diagnostic radiologist of follow-up MRI imaging
- Overall survival

Radiographic MRI outcomes will be assessed by a diagnostic radiologist using standard criteria for radiation treatment effects and disease recurrence. Imaging sets will typically include T1-weighted sequences (with and without gadolinium), T2- and Flair-weighted sequences, and also perfusion, ADC ("apparent diffusion coefficient"), and spectroscopic imaging studies.

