4.2 Treatment Regimen

Prior to the day of treatment, each patient will receive an orientation to the hyperbaric chambers located in the hyperbaric medicine department within radiation oncology. A “test drive” will be performed with the patient in the chamber with air rather than 100% oxygen. This will verify the patient’s ability to equalize pressure in the middle ear and will assure that he or she is not claustrophobic. A small percentage of patients (estimated at 15%, based on prior experience) may be unable to achieve pressure equalization in the middle ear. These patients will be offered placement of a tympanostomy tube to facilitate HBO treatment and to enable continuation with the protocol, a simple procedure performed typically by a Physician’s Assistant in DHMC’s Section of Otolaryngology.

On the day of SRS, during HBO treatment the patient will receive oxygen under pressure while lying supine inside the hyperbaric chamber. HBO will be given at 2.4 ATA. Compression will occur at 3.77 feet/minute. The patient will stay at depth for 30 minutes. Decompression will be performed over a 5-minute time span.

Patients then will be transported from the HBO chamber via stretcher to the SRS treatment area while receiving 100% oxygen via non-rebreather face mask @15L/minute to help maintain oxygen saturation.

Patients then will receive radiosurgery for their metastases as detailed below (Section 5.3 – “SRS Treatment Visit”).

A stopwatch will be used to document the time elapsed from when the patient exits the hyperbaric chamber to when he/she starts receiving SRS (“beam-on”). The goal of this time interval should be kept at ≤ 15 minutes. Elapsed time from leaving the hyperbaric chamber to completion of SRS will be recorded as well.

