6.1 Statistical Methods

For the primary outcome variable of feasibility, the twenty evaluable patients will be analyzed on the basis of the amount of time required from leaving the HBO chamber to beginning SRS for the target lesion (T1).

The goal for each patient (as discussed in Section 2.2) is for T1 to be no greater than 15 minutes. In a Phase I trial of HBO treatment in coordination with fully fractionated head-neck cancer XRT, DHMC established a track-record of an average of only eight minutes from time of leaving the HBO chamber to “beam on” for this patient group [22]. However, set-up for SRS treatment is more complex, involving placement of a head-frame and performance of a CT-scan prior to SRS treatment. These may extend the time interval required for patient set-up after leaving the HBO chamber.

We anticipate a learning curve for the team members of this study. Therefore, stopping rules are as outlined in Section 7.4: no more than 20% of first ten patients treated within

30 minutes of HBO; and no more than 33% of first fifteen patients treated within 30 minutes of HBO.

The primary endpoint of feasibility is defined as having been achieved if more than 50% of the 20 evaluable patients start SRS treatment within 30 minutes of leaving the HBO tank: in other words, T1 is ≤ 30 minutes for $>50\%$ of evaluable patients.

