14.1 Table summarizing study procedures/flowchart

Visit sequence	Type	Description	Data/Activities
#1	Initial consultation visit	Consults with radiation oncology and neurosurgery	H+P** Protocol screening (check inclusion/exclusion criteria, including pathology/radiology) Protocol consent Bloodwork (CBC, CMP, pregnancy test if indicated) Optional biomarker blood draw Chest imaging if indicated (per section 3.1)
#2	Pre-treatment visit	HBO and SRS preparation	Patient familiarized with HBO technique ("dry run" through the HBO chamber) RT-planning brain MRI VisionRT open face mask fitting CT-based simulation for SRS planning
#3	SRS treatment visit	HBO and SRS treatments	HBO SRS to brain metastases (beam-on goal within 15 minutes after leaving HBO decompression)
#4+	Follow-up visit	Follow-up visits – the first 4-6 weeks after SRS, then every 3 months for two years, then every 4 months for one year, then every 6 months for two years, then annually. Individuals in the substudy for biomarkers will have an additional follow-up the day after the SRS treatment visit.	H+P** Brain MRI Bloodwork at first follow-up visit (CBC, CMP) Optional biomarker blood draw

** Note: All history/physical exam evaluations will include vital signs, performance status, neurological exam, mini-mental status exam, and QOL assessments (EORTC Quality of Life C-30 and BCM20).

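### Local outcomes are counted per patient with no defined index lesion, so the comparison with matched controls can be confounded by the number of treated metastases

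*Combined protocol and SAP*

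**What the plan says.** **Number of lesions.** Section 3.1 limits the diameter of the presenting lesion to 5.0 cm but sets no limit on how many metastases a patient may have. Section 4.2 says "Patients then will receive radiosurgery for their metastases as detailed below", after a single HBO exposure. The visit table in section 14.1 lists, for the one treatment visit, "SRS to brain metastases (beam-on goal within 15 minutes after leaving HBO decompression".

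**Local outcomes.** Section 2.3 lists "Incidence of repeat SRS to the index site" as a secondary endpoint, separately from repeat SRS to a distant site. No section defines the index site. Section 6.1 analyses the first occurrence, and the time to it, of events that include recurrence at the SRS site, radionecrosis at the SRS site, and a second or third SRS classed as local or distant. The analysis is on the group of 20, so the unit is the patient.

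**Matching and quotas.** Section 6.1 matches 1:1 on histology, resection status, GPA and size (below or above 2.0 cm), in that order. Number of brain metastases is one component of GPA. If no exact GPA match exists, a control with a higher GPA is taken. Section 6.2 fills four cells of five patients by size and resection status. Section 3.4.3 uses the same two features to replace withdrawn patients.

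**Timing.** Section 6.1 introduces T1 as "the amount of time required from leaving the HBO chamber to beginning SRS for the target lesion (T1" and then declares feasibility if "more than 50% of the 20 evaluable patients start SRS treatment within 30 minutes of leaving the HBO tank". Section 2.2 says feasibility "requires that a patient at least begin SRS within 30 minutes of leaving the HBO chamber".

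**The concern.** If a patient has three treated sites and the analysis takes the first local event at any of them, that patient has three chances of an event where a single-lesion patient has one. A difference in lesion number between the 20 trial patients and their 20 controls would then appear as a difference in local recurrence, radionecrosis or local repeat SRS. These are the outcomes on which a radiosensitizer should show benefit or harm.

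Two gaps follow from the same omission. A patient with one resection cavity and one intact lesion fits two quota cells and two matching categories, and no rule chooses between them. Repeat SRS to a second lesion treated in the same session is neither clearly at the index site nor clearly at a distant site.

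GPA matching limits the imbalance in lesion number but does not remove it. Equal scores can come from different component profiles, and the score itself may be matched inexactly.

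**Working it through.** **1. The plan's own power figure.** Section 6.2 gives a detectable relative risk of 0.39 (control median 6 months, one-sided 0.05, power 0.80). Assumptions for the check: 20 versus 20, exponential survival, 24 months of follow-up each.
- Events needed (Freedman): (1.645 + 0.842)² × [(1 + 0.39)/(1 − 0.39)]² = 32.1.
- Events expected: 20 × (1 − 2^(−24/6)) + 20 × (1 − 2^(−0.39 × 24/6)) = 18.75 + 13.2 = 32.0.
- The figure reproduces (power 0.799). It does not involve lesion number, so this point leaves that arithmetic unchanged.

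**2. Per-patient risk by number of treated lesions.** Input: Table 1 in section 1.1, one-year freedom from local recurrence 85.5% for all subjects, so q = 1 − 0.855 = 0.145. It is used here, as an assumption, as a per-lesion rate.
- Independent lesions: risk = 1 − 0.855ⁿ.
- n = 1: 14.5%.
- n = 2: 1 − 0.7310 = 26.9%, an increase of 12.4 points.
- n = 3: 1 − 0.6250 = 37.5%, a further 10.6 points.
- Fully dependent lesions: 14.5% for every n.
- With the rate for tumors above 2.0 cm (79.2% free, q = 0.208), independence gives 20.8%, 37.3% and 50.3%.

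The true value for a given n lies between the dependent and independent limits if lesions within a patient are non-negatively correlated.

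**3. What an imbalance could do to the test.** Assume that the local-event hazard is proportional to lesion count, that mean count is 1.5 times higher in the trial group, and that HBO has no effect. The apparent hazard ratio is then 1.5. The chance that a one-sided 0.05 test signals harm is Φ(ln 1.5 × √(d/4) − 1.645), with d the number of events:
- d = 10: Φ(0.641 − 1.645) = 0.16.
- d = 20: Φ(0.907 − 1.645) = 0.23.

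Both exceed the nominal 0.05. An imbalance the other way would flatter the HBO group. That error cannot be put as a false non-inferiority rate, because the plan states no margin.

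**4. Timing.** "Total time for treatment to one isocenter" is put at 10 minutes in section 2.2 (3 arcs × 2 + 2 set-ups × 2). If lesions use separate isocenters with no gap and the first beam-on meets the 15-minute goal, later isocenters start at 25 and 35 minutes. Only a third or later one would pass 30 minutes. This matters only if T1 is read as time to a particular lesion.

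**The case against.** The strongest reply has three parts.

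**Lesion count is already controlled, because it is part of GPA.** This stands in part. GPA matching narrows the difference, and calling lesion count unmatched would be wrong. But the control is indirect, and a higher-GPA control may be substituted. The documents do not give the component weights, so neither the size nor the direction of the remaining imbalance can be stated.

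**The 14.5% is not a per-lesion rate.** This stands as a limit on the size. Table 1 is reported by subject and comes from a postoperative series, whereas half of the planned sample has intact lesions. One-year survival there was 52.5%, so a freedom-from-recurrence estimate probably overstates the events that would be observed. A shift of 11 to 12 points also needs independent lesions and a one-lesion average imbalance, neither of which the documents support. It is an upper illustration.

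**Several lesions per session is inferred from plural wording.** That is fair: other places use the singular, and section 2.3 does set recurrence at the treatment site against recurrence elsewhere in the brain. But no section excludes several treated lesions, and the use of lesion count within GPA shows that counts are expected to vary.

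A reader might also infer that the primary endpoint has two conflicting definitions and could change its result according to which lesion is called the target. The documents do not support this. Section 6.1 itself equates T1 ≤ 30 minutes with patients who "start SRS treatment within 30 minutes of leaving the HBO tank". Sections 2.2, 4.2, 5.3.6, 14.1 and 14.3 all time to the start of SRS or beam-on. The target-lesion phrase is a stray one.

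**Conclusion.** The concern holds for the secondary local outcomes. As written, the comparison with controls counts first local events per patient, leaves the index site undefined, and controls lesion number only indirectly, so local recurrence, radionecrosis and local repeat SRS can be confounded by the number of treated lesions. For one-year local recurrence the illustrative range is 14.5% per patient under full dependence, up to 26.9% or 37.5% for two or three independent lesions. That rests on a resected-series rate used per lesion. The actual bias depends on an imbalance that cannot be known from the documents.

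The primary endpoint is not affected. Timing T1 to an index lesion would change that endpoint and put section 6.1 at odds with the other timing sections. This is a should-fix for the secondary analysis and a small wording correction for T1.

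**What to change.** **In section 6.1:**
- At planning, designate one index lesion per patient: the lesion whose size and resection status assign the quota cell and the match. Apply the same rule to controls, using pre-treatment information and without sight of outcomes. Use this definition for the index site in section 2.3.
- Make local recurrence, radionecrosis and local repeat SRS at the index lesion the main local comparison in both groups. Report events at other treated lesions alongside, so that no safety information is lost.
- Among controls tied on the four matching variables, choose the one nearest in number of treated lesions, or in number of brain metastases if the treated count is not held. Tabulate the count in both groups.
- For T1, keep start of SRS (first beam-on) as the primary endpoint and delete the reference to the target lesion. Beam-on for the index lesion may be recorded as a descriptive time.

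**Cost.** Wording, plus case report form fields for the index lesion and the number of lesions treated; number of brain metastases is already needed for GPA. Treatment and sample size do not change. Index-only counting yields fewer events, and it needs the control database (Study 00030625) to identify the site of each event. If the database cannot do so, keep per-patient counting in both groups and rely on the lesion-count tie-break. That is weaker, because it acts only where more than one control is tied.

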Objectives	To demonstrate that coordination of HBO with SRS treatments is feasible. To demonstrate that outcomes for patients treated with combination of HBO and SRS are non-inferior to historical controls.
Number of Subjects	20 evaluable participants
Diagnosis and Main Inclusion Criteria	Patients with brain metastases referred for SRS
Study Product, Dose, Route, Regimen	Hyperbaric oxygen given at 2.4 ATA for 30 minutes immediately prior to SRS
Duration of administration	HBOT for 30 minutes
Reference therapy	SRS without prior HBO
Statistical Methodology	Prospective Phase-I trial (“proof-of-principle”) with matched historical controls

1 Introduction

This document is a protocol for a human research study. This study is to be conducted according to US and international standards of Good Clinical Practice (FDA Title 21 part 312 and International Conference on Harmonization guidelines), applicable government regulations and institutional research policies and procedures.

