Risks: The main risks of hyperbaric oxygen therapy are barotrauma to the ear, claustrophobia, and oxygen-induced seizures. Ear barotrauma, if it occurs, is not life threatening and resolves with time. Patients with claustrophobia requiring treatment will be offered lorazepam to help with confinement anxiety and will have the opportunity to experience the hyperbaric chamber prior to the treatment day. Patients are at small risk for increased seizure activity since high oxygen levels can produce seizures, although usually at levels higher than planned for this study. For the level of oxygen used in this study (2.4 ATA) the incidence in the general population receiving HBOT is about 0.06% or 6 per 10,000 dives [23].

HBO may also contribute to the risk of radiation-related complications. In his review and meta-analysis of hypoxic modification of radiotherapy in head-and-neck cancer patients, Overgaard identifies eight trials that studied HBO in comparison to normal treatment controls. These showed a significant increase in the risk of radiation-related complications, with an odds ratio of 2.43 (CI 1.43-4.12, p<0.01). However, Overgaard hastens to add that the late tissue damage observed with HBO arose in trials where the radiation technique was – even absent HBO – known to have a relatively high likelihood of late toxicity; and the difference in some of the trials was further exacerbated by administering high doses per fraction in the HBO arm but conventional doses per fraction

in the control arm, further confounding the results. Overgaard concludes, “Consequently, there is no definitive evidence of any excess morbidity associated with the [HBO] hypoxic modification itself...” [11]

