In general, the target dose to the margin of the PTV will be prescribed as per RTOG 90-05, which is considered the current standard of care [28]. However, the target dose may be modified to respect normal tissue tolerances (see below), as per clinical judgment of the prescribing radiation oncologist and the consulting neurosurgeon:

Target diameter	Dose to target margin
Up to 2.0 cm	20 Gy
2.1 – 3.0 cm	18 Gy
3.1 – 4.0 cm	15 Gy
4.1 – 5.0 cm	12 Gy

5.3.8 Normal Tissue Tolerance:

Dose prescriptions will take into account the tolerances of surrounding normal tissues, such as brainstem, optic nerves, optic chiasm, and motor cortex. Target dose to the margin of the PTV may be modified to avoid excess dose to such sensitive tissues, per the clinical judgments of the prescribing radiation oncologist and the consulting neurosurgeon.

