For the secondary endpoints, using Cox proportional hazards models, and Kaplan-Meier survival statistics, the overall group of 20 will be analyzed for event-free survival and compared against a matched set of patients from our institution (see below for methodology). This match will be based on tumor size, resection status, and histology-specific graded prognostic assessment (GPA). The GPA is a validated, widely accepted prognostic scale predictive of survival for patients presenting with brain metastases. Diagnosis-specific GPA calculation is based on published criteria including tumor histology, presence of systemic metastases, number of brain metastases, age, performance status, and breast-cancer specific molecular markers [29-31]. Further demographic and treatment data will also be collected, including: gender, subtotal resection versus gross total resection (if tumor resected), tumor diameter (prior to first treatment, whether surgery or SRS), SRS target volume (PTV), and prescribed dose to the PTV. The secondary outcome variables will be the first occurrence of the event of interest and also the time until the first occurrence of the event of interest. These events include: intracranial recurrence at SRS site, intracranial recurrence at a distant site, whole brain XRT, second SRS (classified as either local or distant), third SRS (classified as local or distant), radionecrosis at the SRS site, and death.

A retrospective database pertaining to Dartmouth-Hitchcock's experience with stereotactic radiosurgery in the treatment of brain metastases is being collected through Study 00030625 (PI [name]). Pertinent matching variables, along with demographic variables, treatment variables, and outcome variables for the control population are available on 00030625. The matching variables (histology, lesion size, resection status, and calculated GPA) will be used to identify a control population in the Study 00030625 that match 1:1 against the D12129 enrolled patient population.

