Specifically, patients with similar tumor histologies will be matched against histologies found in the D12129 patient population, falling into one of six categories: (1) non-small cell lung cancer, (2) melanoma, (3) breast cancer, (4) renal cell cancer, (5) GI cancers, and (5) other histologies. Once a histologic match is identified, the patient is then matched by resection status (either unresected or resected). The third matching variable is then GPA. If an exact GPA match is not available in the 000030625 data base, then a patient with a higher GPA will be selected, with the control patient's GPA as near as possible to that of the corresponding D12129 patient (thereby, if anything, biasing the survival outcome data slightly against the D12129 data set). Lastly, the fourth matching variable is tumor size (i.e. maximum tumor diameter) at time of treatment (a categorical variable, either below or above 2.0 cm). If an exact match for the fourth variable is not available in the 000030625 data base, then size will be matched as closely as possible to the 2.0 cm cut-off from those patients available in this historical database. These

matching patients identified in 000030625 data base will serve as the control group for the D12129 study.

Once the control group patients have been selected, their data will be extracted from the 000030625 database in de-identified form. These data will be reviewed by an “honest broker” to assure proper de-identification and HIPAA compliance. These de-identified control group data will then be merged with the D12129 dataset. Analysis of this combined data base then will allow comparison of HBO-treated and control patients in terms of event-specific outcome parameters, with events including: death, local intracranial recurrence, distant intracranial recurrence, whole brain radiation therapy, and repeat SRS (either local or distant).

Exploratory variables will include QOL data and tumor markers. Comparisons for change in markers before versus after HBO-SRS treatment will be performed for the entire group of twenty patients. Also comparisons will be performed for subgroups (including comparisons of those with resections versus those without, and of those above 2.0 cm diameter versus those below).

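### Size is matched only at 2.0 cm and recorded dose has no role in section 6.1, so a correctly matched pair can differ by up to 6 Gy in table dose

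*Combined protocol and SAP*

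**What the plan says.** The Study Summary describes a "Prospective Phase-I trial (“proof-of-principle”) with matched historical controls". For the secondary endpoints, section 6.1 sets out the comparison as follows.

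- **Matching, 1:1.** "The matching variables (histology, lesion size, resection status, and calculated GPA) will be used to identify a control population". Histology comes first, then resection status, then GPA. Size comes last, as "a categorical variable, either below or above 2.0 cm", and may be relaxed if the control database holds no exact match.
- **Data without a stated use.** Further items are collected, among them "SRS target volume (PTV), and prescribed dose to the PTV". Section 6 does not mention dose again.
- **Model.** "using Cox proportional hazards models, and Kaplan-Meier survival statistics, the overall group of 20 will be analyzed for event-free survival". No covariate is named.
- **Outcomes.** The event list includes recurrence at the SRS site and "radionecrosis at the SRS site, and death".

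Section 5.3.7 sets dose by target diameter: 20 Gy up to 2.0 cm, 18 Gy for 2.1–3.0 cm, 15 Gy for 3.1–4.0 cm and 12 Gy for 4.1–5.0 cm. It adds that "the target dose may be modified to respect normal tissue tolerances (see below), as per clinical judgment of the prescribing radiation oncologist"; a neurosurgeon shares in that decision.

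**The concern.** For a radiosensitizer, local recurrence and radionecrosis are the outcomes closest to delivered dose. The controls are historical, so only matching or modelling can make the groups comparable on dose. The size match uses two classes and the dose table uses four bands, so two patients who satisfy every matching rule can belong to different dose bands.

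If the HBO patients happened to have the larger lesions within the upper class, they would have lower table doses. Local control could then look worse, and any added necrosis could be masked. The opposite imbalance would do the reverse. As written, the plan would neither reveal such an imbalance nor show how much it matters.

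**Working it through.** **1. The plan's own figure.** Section 6.2 states a detectable relative risk of 0.39 (one-sided 0.05, power 0.80, control median 6 months). With 20 per group, exponential survival and 24 months of follow-up:

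- events at HR 0.39 = 20 × (1 − 2^(−4)) + 20 × (1 − 2^(−0.39×4)) = 18.75 + 13.2 ≈ 32;
- Freedman's formula then gives a detectable HR of 0.389.

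The figure reproduces. It concerns event-free survival overall and is not affected by this point.

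**2. Dose gap within a pair.** This assumes an exact size match, the 5.3.7 table applied to both members, and the same diameter used for matching and for dosing.

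| Size class in matching | Table doses possible | Largest gap |
|---|---|---|
| Up to 2.0 cm | 20 Gy | 0 |
| Above 2.0 cm | 18, 15, 12 Gy | 18 − 12 = 6 Gy |

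A relaxed match may cross 2.0 cm and bring in the 20 Gy band. Changes for normal tissue tolerance come on top. Neither is counted here.

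**3. Ceiling on the group mean.** Section 6.2 plans 10 patients above 2.0 cm and 10 at or below. If every larger pair differed by 6 Gy in the same direction, the mean difference would be (10 × 6 + 10 × 0)/20 = 3 Gy. A mean of 2 Gy needs 2 × 20/10 = 4 Gy on average across the larger pairs; 1 Gy needs 2 Gy.

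**4. Size and dose together, from the documents.** The Figure 4 legend in section 1.1 gives one-year control of 87.3% in medium lesions (mean 19.2 Gy) and 65.5% in large ones (mean 15.7 Gy). The ratio of cumulative hazards is ln(0.655)/ln(0.873) = 0.423/0.136 ≈ 3.1, over 19.2 − 15.7 = 3.5 Gy. This mixes size with dose and counts lesions, so it is not a dose effect. It does show that the gradient a coarse size match leaves open is not trivial.

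**5. Dose alone, by assumption.** The documents give no dose-response slope. Suppose each extra Gy multiplies the local-recurrence hazard by 0.85 to 0.95. With no HBO effect, the apparent HR is slope^(difference):

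| Mean difference | HBO group higher | HBO group lower |
|---|---|---|
| 1 Gy | 0.85–0.95 | 1.05–1.18 |
| 2 Gy | 0.72–0.90 | 1.11–1.38 |
| 3 Gy (ceiling) | 0.61–0.86 | 1.17–1.63 |

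**6. Against the noise.** Table 1 gives freedom from local recurrence of 85.5% at one year and 66.9% at two. In 40 patients, ignoring deaths, that is 40 × 0.145 = 5.8 to 40 × 0.331 = 13.2 events. Table 1 is a resected series, whereas half of this trial is planned as intact lesions.

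- SE(log HR) ≈ 2/√D: 0.82 with 6 events, 0.55 with 13.
- 95% limits: a factor of about 5 (6 events) or 3 (13 events) either way.
- Largest bias in step 5: |ln 0.614| = 0.49, or 0.49/0.55 ≈ 0.9 SE with 13 events.
- False-positive rate for a one-sided 5% test of benefit, Φ(√(D/4) × |ln HR| − 1.645), D = 13: about 14% at an apparent HR of 0.73 and 23% at 0.61.

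The documents give no radionecrosis rate, so the same sum cannot be done for that outcome.

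**The case against.** **Adjustment is not ruled out.** Section 6.1 plans Cox models and lists dose as a recorded variable in the same paragraph. This stands: the role of dose is unspecified, and it would be wrong to say that the plan rejects adjustment.

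**Prescriber knowledge.** A reader might infer that clinicians in an open-label study will shift dose because the patient is receiving HBO. The documents do not support this. Sections 5.3.7 and 5.3.8 tie changes to normal tissue tolerance, and nothing links them to HBO. That stated reason also points to reductions, not increases. The case here rests on the mismatch between the size classes and the dose bands, which needs no such behavior.

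**Earlier HBO trials.** A reader might take section 1.5 as conceding the same fault in past studies. Its words are "administering high doses per fraction in the HBO arm but conventional doses per fraction" in the control arm of some trials. That is a difference in fractionation, and SRS is a single fraction. Likewise, the 12.65 versus 11.70 Gy trial in section 1.4 says nothing about imbalance here.

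**Small beside the noise.** Under the assumed slopes, the bias stays below one standard error even at the 3 Gy ceiling, and the outcomes are secondary in a 20-patient proof-of-principle study. This stands. It limits how much weight the point carries, but not the value of a nearly free remedy.

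**Dose stands in for size.** Table dose falls with diameter, so a model with raw dose alone would largely adjust for size. Dose is also set after HBO treatment is decided. Both stand and shape the fix.

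**Availability and scope.** Section 6.1 says treatment variables exist for controls but does not name dose. Radionecrosis is in its event list but missing from its closing list of comparisons. Both need confirming.

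**Conclusion.** The point holds as a gap in the matching and analysis rules for the secondary comparison. A pair that meets every rule can differ by up to 6 Gy in table dose, and correspondingly in size; by table, the group mean difference cannot exceed 3 Gy. These limits assume exact size matching, the planned 10/10 size split, the same dose table for controls, and one diameter serving both purposes.

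Whether any imbalance will arise, and in which direction, is unknown. The apparent hazard ratios of 0.61 to 1.63 rest on an assumed slope and illustrate what is possible; they are not predictions. Local recurrence and radionecrosis are the outcomes exposed. The primary feasibility endpoint and the 0.39 in section 6.2 are untouched.

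**What to change.** Amend section 6.1 in three places.

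1. **Tie-break.** Among controls equal on the four stated matching variables, choose the one closest in diameter and in 5.3.7 dose band. Both are fixed by lesion size, so this does not match on anything decided after HBO. It helps only where ties exist, and the documents do not give the size of the control database.
2. **Description.** Tabulate prescribed dose, and its deviation from the table value for that size, by group. First confirm that Study 00030625 holds dose and the relevant diameter. The deviation separates discretionary change from size.
3. **One sensitivity analysis.** Pre-specify a Cox model for local recurrence and for radionecrosis with a single dose term, preferably deviation from the table value or dose band, shown beside the unadjusted result. Confirm that radionecrosis is among the HBO-versus-control comparisons.

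The cost is wording, plus an extraction check for controls. Adjustment also costs precision: if dose explains a share R² of group membership (not given; take 0.05 to 0.30), the standard error grows by 1/√(1 − R²), or 1.03 to 1.20. With about 6 to 13 local recurrences there is room for at most one covariate, so the adjusted result is supportive only. No change to any dose is proposed.
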